2.2 Endpoints

2.2.1 Primary Efficacy Endpoints

There will be two co-primary measures of efficacy for Induction of Clinical Remission and Endoscopic Response. The first co-primary endpoint is:

 Clinical symptom remission defined by (1) the total number of liquid/very soft stools for the 7 days prior to the Week 16 visit being ≤ 10 (from CDAI Item 1); AND (2) an abdominal pain rating of ≤ 1(from CDAI Item 2) on each day for the 7 days prior to the Week 16 visit.

The second co-primary endpoint is:

 Endoscopic response defined as a ≥ 3-point decrease in the SES-CD from baseline to the SES-CD score obtained between Week 16 and Week 17. SES-CD scores will be calculated from centrally-read digital video of ileocolonoscopies performed at baseline and between Week 16 and Week 17.

Confidential

For the daily stool data, the number of daily liquid/very soft stools with a consistency of a Bristol Stool Form Scale [BSFS] score of Type 6 or Type 7 will be assessed using the information recorded by the subject via an electronic diary system. The number of liquid/very soft stools in a given week will be calculated as follows:

(Number of liquid/very soft stools during that week ÷ Number of days with nonmissing assessments during that week) × 7

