6.1.4 Visit 7: Week 16/Day 112 (± 3 days)

The following assessments are to be completed at Visit 7:

- Adverse events and concomitant medications
- Vital signs and weight
- Electrocardiogram
- Full physical examination including disease specific examination (including assessments for abdominal mass and extraintestinal manifestations of Crohn's disease based on CDAI see Appendix 2).
- Safety laboratory tests (hematology, blood chemistry, urinalysis)
- Urine pregnancy test
- Blood for inflammatory markers
- Stool collection and processing. NOTE: If the subject cannot produce a sample during the
 visit, the subject will be issued a collection kit and asked to collect a specimen at home,
 refrigerate it immediately, and bring it to the clinic as soon as possible.
- Stool and Blood collections for Long-term Storage
- CDAI assessment (CDAI score will be calculated by EDC system)
- IBDQ and WPAI-CD
- Review dosing and diary compliance
- Study drug collection and dispensing

Confidential

- Schedule ileocolonoscopy and dispense bowel prep for ileocolonoscopy
 - Ileocolonoscopy to be performed within 7 days after Visit 7.
 - All Visit 7 procedures to be completed prior to beginning bowel prep.
- Schedule Visit 8
- 6.1.5 Visits 8, 9, 10, 11, 12, 13, 14, 15: Weeks 20, 24, 28, 32, 36, 40, 44, 48 /Days 140, 168, 196, 224, 252, 280, 308, 336 (±3 days)

The following assessments are to be completed:

- Adverse events and concomitant medications
- Vital signs and weight
- Disease and symptom driven physical examination (including assessments for abdominal mass and extraintestinal manifestations of Crohn's disease based on CDAI – see Appendix 2)
- Safety laboratory tests (hematology, blood chemistry, urinalysis) with urine pregnancy test at Visit 10 (Week 28) and Visit 13 (Week 40) only, blood draw for PK at Visit 15 only
- At Visit 15 only: Record time and date of most recent dose of study drug. This
 information must be obtained from the subject and should be his/her best recollection of
 when they took their most recent dose.
- CDAI assessment (CDAI score will be calculated by EDC system)
- IBDQ and WPAI-CD at Visit 10 (Week 28) and Visit13 (Week 40) only
- Review dosing and diary compliance
- Study drug collection and dispensing
- Schedule the next study visit (Visit 15 should occur in the morning)

6.1.6 Visit 16: End of Treatment (EOT) Visit, Week 52/Day 364 (± 3 days)

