The subject's final dose of study drug will be the evening before Visit 16. The following assessments are to be completed at this visit:

- Adverse events and concomitant medications
- Vital signs and weight
- Electrocardiogram
- Full physical examination including disease specific examination (including assessments for abdominal mass and extraintestinal manifestations of Crohn's disease based on CDAI see Appendix 2).

Confidential

- Safety laboratory tests (hematology, blood chemistry, urinalysis) including blood for serum pregnancy test and inflammatory markers
- Stool collection and processing. NOTE: If the subject cannot produce a sample during the
 visit, the subject will be issued a collection kit and asked to collect a specimen at home,
 refrigerate it immediately, and bring it to the clinic as soon as possible.
- · Stool and Blood collections for Long-term Storage
- CDAI assessment (CDAI score will be calculated by EDC system)
- IBDQ and WPAI-CD
- Review dosing and diary compliance
- Collect unused study drug
- Schedule ileocolonoscopy and dispense bowel prep for ileocolonoscopy
 - Ileocolonoscopy to be conducted within 7 days after Visit 16.
 - All Visit 16 procedures to be completed prior to beginning bowel prep.
- Schedule Visit 17, EOS

6.1.7 Visit 17: End of Study (EOS) Visit, Week 54/Day 378 (± 3 days)

The following assessments are to be completed:

- Adverse events and concomitant medications
- Vital signs and weight
- Electrocardiogram
- Safety laboratory tests (hematology, blood chemistry, urinalysis)

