8.6.1 Primary Efficacy Analysis

Induction Phase

There will be two co-primary measures of efficacy assessed during the Induction Phase. The first co-primary endpoint is:

 Clinical symptom remission defined by (1) the total number of liquid/very soft stools for the 7 days prior to the Week 16 visit being ≤ 10 (from CDAI Item 1); AND (2) an abdominal pain rating of ≤ 1(from CDAI Item 2) on each day for the 7 days prior to the Week 16 visit.

The second co-primary endpoint is:

 Endoscopic response defined as a ≥3-point decrease in the SES-CD from baseline to the SES-CD score obtained between Week 16 and Week 17. SES-CD scores will be calculated from centrally-read digital video of ileocolonoscopies performed at baseline and between Week 16 and Week 17.

For each endpoint, the null hypothesis H0: πR - πP =0 versus the alternative HA: πR - $\pi P \neq 0$ is of interest, where πR is the binomial parameter for induction of remission/response for the

Rifaximin DR group, and πP is the binomial parameter for induction of remission/response for the placebo group. Subjects who require the initiation of rescue medication and/or surgery for CD will be considered treatment failures from the date of the introduction of the rescue medication and/or surgery, regardless of their actual response data. The Cochran-Mantel-Haenszel (CMH) test, stratified by country, will be used to test the hypothesis. Each null hypothesis of no difference will be rejected if the resulting p-value for the respective statistical test is less than 0.05. Significance for the induction claim will only be declared if both null hypotheses are rejected. As such, the overall Type I error rate will be maintained at the 5% level without adjustment for multiple comparisons.

If it is evident that the response variable is confounded with some of the background variables, then logistic regression will be performed using the background variables as covariates. The differences between this adjusted analysis and the previous unadjusted analysis will be noted, and the impact of such differences will be discussed.

The primary efficacy analysis will be repeated on the PP population to assess the robustness of the results of the primary outcome.

Long Term Treatment Phase

There will be two key co-secondary endpoints of efficacy assessed during the Long Term Treatment Phase. The first is:

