 Clinical symptom remission defined by (1) the total number of liquid/very soft stools for the 7 days prior to the Week 52 visit being ≤ 10 (from CDAI Item 1); AND (2) an abdominal pain rating of ≤ 1 (from CDAI Item 2) on each day for the 7 days prior to the Week 52 visit.

The second is:

 Endoscopic remission defined as a SES-CD score of ≤ 2 at Week 52. SES-CD scores will be calculated from centrally-read digital video of ileocolonoscopies performed at Week 52.

For each endpoint, the number and proportion of subjects with clinical and endoscopic remission will be summarized by treatment group for the ITT Population.

For each endpoint, the null hypothesis H0: $\pi R - \pi P = 0$ versus the alternative HA: $\pi R - \pi P \neq 0$ is of interest, where πR is the binomial parameter for remission for the Rifaximin DR group, and πP is the binomial parameter for remission for the placebo group. Subjects who require the initiation of rescue medication and/or surgery for CD will be considered treatment failures from the date of the introduction of the rescue medication and/or surgery, regardless of their actual response data. The Cochran-Mantel-Haenszel (CMH) test, stratified by country, will be used to test the hypothesis. Each null hypothesis of no difference will be rejected if the resulting p-value for the respective statistical test is less than 0.05. Significance for clinical

and endoscopic remission will only be declared if both null hypotheses are rejected. As such, the overall Type I error rate will be maintained at the 5% level without adjustment for multiple comparisons.

If it is evident that the response variable is confounded with some of the background variables, then logistic regression will be performed using the background variables as covariates. The differences between this adjusted analysis and the previous unadjusted analysis will be noted, and the impact of such differences will be discussed.

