8.7.2 Handling of Dropouts or Missing Data

Missing data will be handled using the Worst Case analysis method for the primary and key secondary endpoints. In the Worst Case analysis, subjects with fewer than 4 days of diary data in a given week will be considered non-responders for that week. Additionally, subjects with missing SES-CD data will be classified non-responder for that measure in that week.

The following three sensitivity analyses will be conducted to address the impact of missing data on the primary and key secondary endpoints:

Last Observation Carried Forward (LOCF) Analysis: In the first analysis, missing values will be replaced with the last previous non-missing value. The baseline values will not be carried forward.

Multiple Imputation Analysis: In the second analysis, missing values will be filled in by the multiple imputation method which involves the following distinct phases:

- The missing data will be filled in to generate complete data sets using SAS/STAT procedure PROC MI;
- The complete data sets will be analyzed using PROC LOGISTIC in SAS/STAT;
- The above two steps will be repeated 5 times;
- The results from the complete data sets will be combined for statistical inferenceusing SAS/STAT procedure PROC MIANALYZE.

Observed Case Analysis: In the third analysis, subjects are excluded from the analysis if the subject has insufficient data to be determined as a responder or non-responder in a given 4-week assessment period. This analysis is not based on the ITT population and, therefore, interpretation of results from this analysis requires substantial caution. This is because the subjects who responded in the respective treatment groups may have different distributions for background characteristics. Thus, additional analysis may be undertaken by the use of statistical methods which provide adjustment for background characteristics.

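### Does the undefined 4-week assessment period in protocol Section 8.7.2 leave the Observed Case analysis without a workable analysis set?

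*Protocol*

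**What the plan says.** Section 8.7.2 handles missing data in the primary and key secondary endpoints by a Worst Case rule. For the diary, "subjects with fewer than 4 days of diary data in a given week will be considered non-responders for that week"; a missing SES-CD is likewise a non-response. The section then adds checks: "The following three sensitivity analyses will be conducted to address the impact of missing data on the primary and key secondary endpoints". The third of these, Observed Case, leaves out subjects with "insufficient data to be determined as a responder or non-responder in a given 4-week assessment period". The protocol warns that this analysis is not based on the ITT population and must be interpreted with much caution.

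The endpoints are fixed in Sections 2.2.1, 2.2.2 and 8.6.1. Clinical symptom remission needs a 7-day liquid or very soft stool total of at most 10, and a pain rating of at most 1 "on each day for the 7 days prior to the Week 16 visit"; the Week 52 version requires the same "on each day for the 7 days prior to the Week 52 visit". The endoscopic endpoints each need a single post-baseline procedure. Section 6.1.4 says "Ileocolonoscopy to be performed within 7 days after Visit 7", and Section 6.1.6 says "Ileocolonoscopy to be conducted within 7 days after Visit 16".

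For incomplete diary weeks, Section 2.2.1 scales the stool count: ("Number of liquid/very soft stools during that week ÷ Number of days with nonmissing assessments during that week) × 7". No matching sentence is written for pain. Section 8.0 leaves computational algorithms and data handling conventions to the statistical analysis plan.

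**The concern.** Section 8.7.2 uses two time units. Worst Case works by the week, and Observed Case by a 4-week period that is defined nowhere and on which no endpoint is scored. Taken literally, the exclusion rule asks for a 4-week responder status that does not exist.

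A subject who stops treatment and diary in the three weeks before the endpoint week shows the difficulty. This subject has diary entries inside a 4-week period but none in the 7 days that count. If the period is taken to end at the visit, the ileocolonoscopy may also lie outside it. Read the opposite way, with adequate data needed in all four weeks, the rule would discard subjects whose endpoint week is complete.

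Observed Case is one of three analyses meant to show whether missing data drive the co-primary and key co-secondary results, so its analysis set should be identifiable before unblinding. A related doubt is whether a week with 4 to 6 diary days counts as insufficient data, given that pain must qualify on each of 7 days.

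**Working it through.** The protocol gives no figure for the size of the Observed Case set, so there is none to reproduce. The check is first a comparison of the texts, then a bound on how many subjects a different reading could move.

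**1. Texts side by side**

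| Item | Unit in the protocol | Section |
|---|---|---|
| Clinical symptom remission | 7 diary days before the Week 16 or Week 52 visit | 2.2.1, 2.2.2, 8.6.1 |
| Endoscopic response or remission | one ileocolonoscopy within 7 days after Visit 7 or Visit 16 | 6.1.4, 6.1.6 |
| Worst Case, diary | a given week | 8.7.2 |
| Worst Case, SES-CD | that measure in that week | 8.7.2 |
| Observed Case | a given 4-week period | 8.7.2 |
| Clinic visits from Week 4 on | every 4 weeks | 6.1.3 to 6.1.6 |

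The last row gives the likely origin of the phrase: it probably names the interval belonging to a visit. The exclusion itself turns on whether responder status can be determined, and that status is defined only on the windows in the first two rows. With no usable endpoint-week diary it cannot be determined, and the subject is excluded. With a usable endpoint week it can be, and the subject stays. The same holds for the endoscopic endpoint and a readable SES-CD.

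**2. Size under a reading that keeps anyone with some diary data in four weeks**

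Inputs: 20% dropout and 330 per arm (Section 8.2); Week 16 is Day 112 and Week 52 is Day 364 (Sections 6.1.4 and 6.1.6). Assumption: a constant dropout rate, so S(t) = exp(−ht) with h = −ln(0.8)/364 = 0.000613 per day. The subjects concerned leave in the 21 days before the endpoint week.

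- Week 16: S(84) − S(105) = 0.9498 − 0.9377 = 0.0121; 330 × 0.0121 = 4.0 per arm.
- Week 52: S(336) − S(357) = 0.8139 − 0.8034 = 0.0104; 330 × 0.0104 = 3.4 per arm.
- If all 20% left by Week 16, h = −ln(0.8)/112 = 0.001992 and S(84) − S(105) = 0.8459 − 0.8112 = 0.0347; 330 × 0.0347 = 11.4 per arm.

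**3. Size under a reading that needs at least 4 diary days in each of four weeks**

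Let q be the chance of fewer than 4 diary days in a week. The chance of a usable endpoint week with at least one short earlier week is (1 − q)(1 − (1 − q)³). Assume 95% daily completion, independent weeks, and a within-week correlation of missing days of 0, 0.2 or 0.5.

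- q = 0.0002, 0.0168, 0.0396.
- Result: 0.1%, 4.9%, 11.0%.

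The larger values need strongly clustered missing days within a week together with independence between weeks, so they are an upper end. Completion and correlation are assumptions, and nothing in Section 8.7.2 asks for four adequate weeks.

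**4. Weeks with 4 to 6 diary days**

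Stools are covered: scaled to 7 days, the largest raw count that still meets the limit of 10 is 5, 7, 8 and 10 for 4, 5, 6 and 7 recorded days. For pain, the 4-day floor points to judging the recorded days. If all 7 were required, any incomplete week would already fail clinical symptom remission, and the floor would do nothing for that endpoint.

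**The case for a change.** The strongest case for a change is that this is not silence left to the analysis plan. The protocol states a time unit, the unit contradicts its own endpoints, and an analysis plan would have to repeat the conflict or depart from it. Correcting the phrase would cost almost nothing. The facts behind that argument stand: the phrase is undefined and matches no primary or key secondary endpoint.

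What does not stand is the step from there to an analysis that cannot be run. The readings that alter the set each add something the text does not say: that any entry in four weeks suffices, that all four weeks must be adequate, or that the period ends at the visit. Without these additions, the rule and a corrected rule exclude the same subjects.

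The pain question is a separate matter. It bears on how the endpoint itself is scored, and it is a data handling convention of the kind Section 8.0 assigns to the analysis plan. The power figures that can be attached to a strict 7-day reading do not help either. At 330 per arm and 95% completion, under the three correlations above, power is 0.82, 0.89 and 0.93 if dropout is ignored. It is 0.68, 0.77 and 0.82 if 20% are counted as failures. Both sets depend on a completion rate and a correlation that the protocol does not give, and on treating the planned 40% and 55% as full-diary rates, which it does not say.

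**Conclusion.** This is a clerical slip in a single phrase, and no change to the plan follows. An analyst applying Section 8.7.2 with the endpoint definitions in Section 8.6.1 arrives at the right Observed Case set: subjects whose status is known on the endpoint's own window.

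If someone instead kept every subject with some diary data in four weeks, about 1% would be handled differently (4 of 330 per arm at Week 16, 3 of 330 at Week 52). That rests on 20% dropout at a constant rate; the figure is 3.5% (11 of 330) in the extreme case of all dropout by Week 16. Applied blind to both arms, either handling gives a fair comparison unless missing data differ by arm.

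Only one of three sensitivity analyses is touched, and the protocol already tells the reader to treat it with caution. The primary analysis, its error control, the sample size and the claims for induction and long-term treatment do not depend on it.

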8.7.3 Interim Analyses and Data Monitoring

No interim analyses are planned for this study.

8.7.4 Multicenter Studies

Centers will be pooled within countries for the assessment of country effects.

8.7.5 Multiple Comparisons/Multiplicity

The study has a single primary endpoint as the primary hypothesis, therefore no multiplicity adjustment is needed to the overall significance level of 0.05. Additionally, the clinical trial will be providing data for two separate indications (induction and long term treatment) with each indication having its own separate endpoint. On that basis, no multiplicity adjustment is needed to the overall significance level of 0.05 per indication because conclusions will be reached independently for induction and separately for long term treatment.

The complete evaluation of clinical efficacy in this study requires the study of multiple key secondary efficacy variables collected at numerous time points. It is therefore necessary to properly and sensitively control the probability of making erroneous conclusions based solely upon compounding the likelihood of a type I error. The issue of multiplicity of secondary measurements will be handled by statistical testing of these outcomes in a hierarchical fashion. The order of secondary endpoints for the Induction and Long Term Treatment Phases are described in Sections 2.2.2 and 2.2.3. Significance tests will be conducted until a non-significant p-value is found (p > 0.05). Once a non-significant p-value occurred, all subsequent significance tests will be considered exploratory in nature.

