2.1.2 Secondary Objectives

A key secondary objective is to evaluate clinical and endoscopic remission following an additional 36-week Long Term Treatment Phase of Rifaximin DR 800 mg BID vs. placebo.

The secondary objectives of this study are the following:

- Assess the safety of Rifaximin DR following a 16-week induction, and an additional 36-week Long Term Treatment Phase (i.e., up to 52 weeks of treatment for eligible subjects).
- Assess the population pharmacokinetics of Rifaximin DR.
- Characterize the gastrointestinal microbiota from stool samples, and antibiotic resistance from bacteria cultured from stool samples before and after treatment with RifaximinDR.
- Evaluate the effects of Rifaximin DR treatment on indices of health outcomes.
- Assess the effects of Rifaximin DR treatment on biological (inflammatory) markers of disease.

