2.2.2 Key Secondary Endpoints

The key secondary endpoint is clinical and endoscopic remission. Two key co-secondary endpoints of efficacy will assess this endpoint during the Long Term Treatment Phase. The first is:

 Clinical symptom remission defined by (1) the total number of liquid/very soft stools for the 7 days prior to the Week 52 visit being ≤ 10 (from CDAI Item 1); AND (2) an abdominal pain rating of ≤ 1(from CDAI Item 2) on each day for the 7 days prior to the Week 52 visit.

The second is:

 Endoscopic remission defined as a SES-CD score of ≤ 2 at Week 52. SES-CD scores will be calculated from centrally-read digital video of ileocolonoscopies performed at Week 52.

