2.2.3 Secondary Efficacy Endpoints

- Induction of clinical remission defined as a CDAI Score of less than 150 points at Week 16.
- Clinical symptom remission over time: The total number of liquid/very soft stools for the
 7 days prior to each clinic visit being ≤ 10; AND (2) an abdominal pain rating of ≤ 1 on
 each day for the last 7 days prior to each clinic visit in ≥ 80% of the study visits during the
 52-Week Treatment Period, including Week 52.
- Time until durable response (see Section 8.6.2) to the liquid/very soft stool component of the co-primary endpoint during the 52-Week Treatment Period.
- Time until durable response (See Section 8.6.2) to the abdominal pain component of the co-primary endpoint during the 52-Week Treatment Period.
- Proportion of subjects with response to the abdominal pain component of the co-primary endpoint at post-baseline time points.
- Proportion of subjects with response to the liquid/very soft stool component of the coprimary endpoint at post-baseline time points.
- Change from baseline in SES-CD score at Week 16 and Week 52.
- Proportion of subjects with SES-CD score of 0 at Week 52.

Confidential

- Proportion of subjects who achieve clinical remission by the CDAI endpoint at postbaseline time points.
- Time to loss of CDAI response defined by a CDAI score of ≥ 150 points during the Long Term Treatment Phase.
- Percentage of subjects who achieve clinical response at post-baseline time points. Clinical response is defined as a reduction of at least 100 points from the baseline CDAI score.
- Time to clinical remission based on abdominal pain and liquid stool components of the coprimary endpoints.
- Time to clinical remission based on CDAI < 150.
- Change from baseline in indices of health outcomes (Inflammatory Bowel Disease Questionnaire [IBDQ], Work Productivity and Activity Impairment Questionnaire for Crohn's Disease [WPAI-CD]) at post-baseline time points.
- Change from baseline in markers of inflammation (e.g. CRP, interleukins, cytokines, fecal calprotectin) at post-baseline time points.

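### Section 8.7.5 promises separate 0.05 conclusions per indication, but its stated order makes Week 16 secondary results depend on the Week 52 pair and not on the Week 16 co-primaries

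*Protocol*

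**What the plan says.** Section 8.7.5 has two paragraphs.

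- The first treats induction and long term treatment as two indications, each with its own endpoint and its own unadjusted 0.05, because "conclusions will be reached independently for induction and separately for long term treatment".
- The second turns to the secondary endpoints: "It is therefore necessary to properly and sensitively control the probability of making erroneous conclusions". The method is a hierarchy: "The issue of multiplicity of secondary measurements will be handled by statistical testing of these outcomes in a hierarchical fashion". Testing stops at the first p above 0.05, and everything after that is exploratory. The sequence is fixed by reference: "The order of secondary endpoints for the Induction and Long Term Treatment Phases are described in Sections 2.2.2 and 2.2.3".

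The two sections named there contain the following.

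- Section 2.2.2 is wholly a Week 52 section: "The key secondary endpoint is clinical and endoscopic remission", assessed by two co-secondary endpoints in the Long Term Treatment Phase. Section 2.1.2 matches: "A key secondary objective is to evaluate clinical and endoscopic remission following an additional 36-week Long Term Treatment Phase".
- Section 2.2.3 is a single list with no division by phase. Its first bullet is "Induction of clinical remission defined as a CDAI Score of less than 150 points at Week 16". Later bullets include SES-CD change at both Week 16 and Week 52, SES-CD of 0 at Week 52, and time to loss of CDAI response in the Long Term Treatment Phase.

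Section 8.6.1 sets the rule for each pair separately: both tests must reject at 0.05. Neither 8.6.1 nor 8.7.5 says that anything in 2.2.2 or 2.2.3 waits for the Week 16 co-primaries.

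**The concern.** If conclusions are separate for each indication, a Week 16 secondary result should stand or fall with the Week 16 primary result. The stated order does something else. It places the Week 16 CDAI result behind the Week 52 pair and leaves it unconnected to the Week 16 co-primaries. Two consequences follow.

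- If Week 16 succeeds and Week 52 fails, a Week 16 secondary becomes exploratory because of a result 36 weeks later in the other indication.
- If Week 16 fails and Week 52 succeeds, the Week 16 CDAI result may still be tested as confirmatory, although the primary objective was not met.

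In the second case induction has a route to a confirmatory claim outside its own 0.05, so the per-indication control that the section relies on is lost. In both cases two readers can give the same result a different status.

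**Working it through.** **1. The plan's own figures reproduce.** With 240 per arm and 40% versus 55%, two-sided 0.05, power is 91.1% per endpoint (Section 8.2 says at least 90%). For both endpoints, 0.911² = 0.830, or 0.90² = 0.81 at exactly 90% (8.2 says about 80%). Within one pair, both-must-reject caps the error at 0.05, as 8.6.1 says.

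**2. Status of the Week 16 CDAI result under the two readings.**

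| Week 16 pair | Week 52 pair | Literal order (2.2.2, then 2.2.3) | Each phase follows its own pair |
|---|---|---|---|
| succeeds | succeeds | testable | testable |
| succeeds | fails | exploratory | testable |
| fails | succeeds | testable | exploratory |
| fails | fails | exploratory | exploratory |

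The readings differ exactly when one pair succeeds and the other does not.

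**3. How often that happens at planned power.** If tests are independent, each pair succeeds with probability 0.81, so exactly one succeeds with probability 2 × 0.81 × 0.19 = 0.308. The protocol gives no correlations, so these were assumed and simulated: four normal statistics, mean 3.24 for 90% power, two-sided 0.05, 4 million draws per setting.

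| Within-pair correlation | Same endpoint, Week 16 to 52 | One given pair succeeds | Both pairs succeed | Exactly one succeeds |
|---|---|---|---|---|
| 0 | 0 | 0.810 | 0.656 | 0.308 |
| 0.3 | 0.5 | 0.822 | 0.713 | 0.218 |
| 0.5 | 0.5 | 0.833 | 0.730 | 0.206 |
| 0.3 | 0.7 | 0.822 | 0.736 | 0.172 |
| 0.5 | 0.7 | 0.833 | 0.752 | 0.162 |

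Half of each last-column figure falls in each of the two middle rows of step 2.

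Section 8.2 gives no Week 52 placebo rate. For assumed placebo rates from 5% to 42.5%, a 15-point effect and 210 per arm, joint Week 52 power under independence is 0.994 to 0.757. With the Week 16 pair at 0.81, exactly one pair then succeeds with probability 0.81 × 0.006 + 0.19 × 0.994 = 0.19 to 0.81 × 0.243 + 0.19 × 0.757 = 0.34.

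**4. Error for the induction indication.** Under the literal order a false induction claim can arise in two ways: the Week 16 pair (at most 0.05), or a Week 16 item of 2.2.3 reached through a successful Week 52 pair (at most 0.05). The bound is 0.05 + 0.05 = 0.10.

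The worst case has one Week 16 co-primary null and the other always significant, the Week 52 pair always successful, and CDAI at Week 16 null. Error is then the chance that at least one of two null tests rejects: 1 − 0.95² = 0.0975 if they are independent, and 0.091, 0.083 and 0.070 at correlations 0.5, 0.7 and 0.9. Counting only results in favour of the drug, it is 1 − 0.975² = 0.049 if independent and 0.035 at 0.9. If Week 16 items are tested only after the Week 16 pair, the cap is 0.05 (0.025 in the direction of benefit). Because the CDAI contains both symptom items, the higher correlations are the more relevant ones when the null co-primary is the symptom endpoint.

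**The case against.** **A stand-alone claim can head its own sequence.** The first step of a fixed sequence is tested at the full 0.05, so the Week 52 pair can be both a separate claim and the start of a hierarchy. This stands. A reader might infer that 8.7.5 gives the pair two incompatible statuses, but its test level is 0.05 either way. The fault lies in what is placed behind it.

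**The sentence on order names both phases, so it may mean an order within each phase.** That reading fits the first paragraph, and it may be what the sponsor intends. The text does not deliver it: 2.2.2 holds only Week 52 endpoints and 2.2.3 is one undivided list, so no order per phase can be extracted.

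**Study-wise error.** A reader might also infer that the protocol promises 5% across both indications and breaks that promise, because 8.6.1 says that "the overall Type I error rate will be maintained at the 5% level without adjustment for multiple comparisons". The documents do not support this. In each half of 8.6.1 the statement follows from that pair's both-must-reject rule, and 8.7.5 states its level per indication. Separate alpha for two indications is a declared and legitimate choice, so a study-wise figure near 10% for the two pairs is not a defect by the plan's own standard.

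**The frequencies are not error rates.** Correct. Step 3 assumes that all four effects are real, so a Week 52 success there is a true one. The figures show only how often the status of a result would be open to dispute.

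**The statistical analysis plan can settle it.** It can add the starting condition. It cannot follow both the independent conclusions and the stated order, because the protocol fixes both.

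**Conclusion.** The point holds as an error in the stated testing order. Section 8.7.5 declares control per indication, then gives an order that ties Week 16 secondary results to the Week 52 pair and leaves them free of the Week 16 co-primaries. The error bound for induction becomes 10% instead of 5%, a worst case that needs Week 52 to succeed while the relevant Week 16 effects are null. At planned power the status of the Week 16 CDAI result is open to dispute in about 31% of trials under independence and 16-22% at the assumed correlations (within pair 0.3-0.5, across time 0.5-0.7), with 90% power taken for every endpoint. It should be corrected before unblinding, because otherwise the reading could be chosen after the results are known. It does not call into question either pair's own test or the choice of 0.05 per indication.

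**What to change.** In Section 8.7.5, keep 0.05 per indication and replace the single order with two.

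- **Induction:** the Week 16 co-primary pair, then the Week 16 items of 2.2.3 in a stated order, tested only if both co-primaries have p < 0.05.
- **Long term:** the Week 52 pair, then the Week 52 and long-term items of 2.2.3 in a stated order, tested only if both Week 52 tests have p < 0.05.
- **Items spanning both phases**, such as SES-CD change at Weeks 16 and 52: assign each to one sequence or split it by time point.
- **In 8.7.5 and 8.6.1:** state that type I error is controlled at 5% per indication and not study-wise.

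The cost is wording only; no patients or data are needed. The Week 52 pair loses no power. Week 16 secondaries become exploratory when the Week 16 pair fails, in about 17-19% of trials at planned power (1 − 0.833 to 1 − 0.810). Under the literal order they are blocked equally often, by a Week 52 failure.

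If the sponsor also wants study-wise 5% control, the Week 52 pair could be tested only after the Week 16 pair succeeds. That is an optional trade-off. It lowers joint Week 52 power by 8 to 15 points in the settings above (0.833 to 0.752 at one end, 0.810 to 0.656 at the other).
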